5.9.1 Progressive Disease

Progressive disease (PD) is defined according to the international uniform response criteria (Durie et al. Leukemia 20:1467-73, 2006, ERRATUM Durie et al. Leukemia 21:1134, 2007) and requires any of the following, confirmed on two consecutive assessments:

An increase of 25% from lowest response value in any one or more of the following:

- Serum M-component (absolute increase must be ≥ 0.5 g/100 ml) *
- Urine M-component (absolute increase must be ≥ 200 mg per 24 h)
- Only in patients without measurable serum and urine M-protein levels: the difference between involved and uninvolved FLC levels (absolute increase must be >100 mg/l)
- Bone marrow plasma cell percentage (absolute % must be $\geq 10\%$)

And / or:

- Definite development of new bone lesions or soft tissue plasmacytomas or definite increase in the size of existing bone lesions or soft tissue plasmacytomas
- Development of hypercalcemia (corrected serum calcium >11.5 mg/100 ml) that can be attributed solely to the plasma cell proliferative disorder

*: If the starting serum m-protein level is ≥ 5 g/dL an absolute increase of ≥ 1 g/dL, verified on two consecutive measurements, is sufficient to define progressive disease.

The decision as to when to repeat the assessment to document progressive disease will be left at the discretion of the treating physician, there is no need to wait until the next scheduled response assessment.

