⁹ Lenalidomide must be prescribed through and in compliance with the RevAssist® program of Celgene Corporation. Prescriptions must be filled within 7 days.

¹⁰ Consideration should be given to prescribing lenalidomide 5 to 7 days in advance of Day 1 of each cycle to allow time for required patient and prescriber surveys, and drug shipment to patient. Any unused Revlimid® (lenalidomide) should be returned to the patient for disposition in accordance with the RevAssist® program. Lenalidomide will be taken by patients from day 1-21 of the 28 day cycle as outlined under 5.6.

¹¹ Azacitidine will be administered at the Taussig Cancer Institute and Case Medical Center as outlined under 5.6, with weekly dosing for dose levels 1 and 2, and twice-a-week administration for dose levels 3 to 5.

¹² Dexamethasone will be taken by patients weekly during cycle 1 to 6 as outlined under 5.6. At day one of each cycle it should be ascertained that patients have an active prescription.

¹³ Response according international uniform response criteria, outlined in section 7. If PD is suspected, response may be re-assessed through repeat of relevant lab tests at any time before the next planned assessment for confirmation.

¹⁴ An additional safety assessment will be done 28 days (+/- 2 days) following the last dose of protocol therapy.

3 Background and Rationale

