5.3 Definition Relapsed Myeloma and Refractory Myeloma

A recent ASH/FDA panel has recommended to include clinical criteria to define relapsed myeloma and to separately analyze data for the relapsed as opposed to the refractory group of patients (56). In accordance with this consensus statement, International Myeloma Working Group diagnostic criteria (57), and the international uniform response criteria (58) the following definitions will be used:

5.3.1 Refractory Myeloma.

Biochemical or clinical evidence of loss of disease control within 90 days after the last therapy. Any of the following defines refractory myeloma:

1. Progressive disease (see 5.8.1) on prior therapy
2. Best response to prior therapy was stable disease (see under 7)
3. Progressive disease (see 5.8.1) within 90 days of the last therapy

5.3.2 Relapsed Myeloma.

Not fulfilling criteria for refractory disease and at least one biochemical **and** at least one clinical criterion fulfilled indicating recurrence of disease more than 90 days after the last therapy:

One or more biochemical criteria for recurrent disease:

An increase of 25% from lowest response value in any one or more of the following, verified on two consecutive measurements:

1. Serum M-component (absolute increase must be ≥ 0.5 g/100 ml) *
2. Urine M-component (absolute increase must be ≥ 200 mg per 24 h)
3. Only in patients without measurable serum and urine M-protein levels: the difference between involved and uninvolved FLC levels (absolute increase must be >100 mg/l)
4. Bone marrow plasma cell percentage (absolute % must be $\geq 10\%$)

AND one or more clinical criteria for recurrent disease:

Any of the following:

1. Definite development of new bone lesions or soft tissue plasmacytomas
2. Definite increase in the size of existing bone lesions or soft tissue plasmacytomas. A definite increase is defined as a 50% (and at least 1 cm) increase as measured serially by the sum of the products of the cross-diameters of each measurable lesion
3. Development of hypercalcemia (corrected serum calcium >11.5 mg / 100ml) that can be attributed solely to the plasma cell proliferative disorder
4. Decrease of hemoglobin by at least 2g/dL below the best independent value (without ESA or blood transfusion for at least 28 days) since the end of previous

therapy or new decrease in HgB below 10g/dL or to 2g/dL below the lower limit of normal

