6.4 Adverse Event Updates/IND Safety Reports

Celgene shall notify the Investigator via an IND Safety Report of the following information:

- Any AE associated with the use of drug in this study or in other studies that is both serious and unexpected.
- Any finding from tests in laboratory animals that suggests a significant risk for human subjects including reports of mutagenicity, teratogenicity, or carcinogenicity.

The Investigator shall notify his/her IRB/EC promptly of these new serious and unexpected AE(s) or significant risks to subjects.

The Investigator must keep copies of all AE information, including correspondence with Celgene and the IRB/EC, on file (see Section 11.4 for records retention information).

7 Response Criteria

Baseline assessments must occur within \leq 7 days of protocol therapy initiation as indicated in Section 2, Schedule of Study Assessments.

Efficacy assessments are scheduled to occur monthly, beginning at Cycle 3 Day 1, during the first 12 cycles, then every two months.

All response categories (60) require two consecutive blood and urine assessments (bone marrow biopsies do not need to be repeated) and no evidence for progressive or new bone lesions if radiographic studies were performed. Radiographic studies are not required for response assessment but should be obtained when there is clinical suspicion for progressive bone disease.

Complete response (CR)	Negative immunofixation of serum and urine (or normal sFLC ratio if the only measurable disease outside of the bone marrow is by sFLCs) and disappearance of any soft tissue plasmacytomas, and <5% plasma cells in bone marrow
Stringent CR (sCR)	CR as defined above plus normal sFLC ratio and absence of clonal cells in bone marrow by immunohistochemistry or immunofluorescence
Very good partial response (VGPR)	Serum and urine M-component detectable by immunofixation but not on electrophoresis or $\geq 90\%$ or greater reduction in serum M-component plus urine M-component <100mg per 24 h or >90% reduction in the difference between involved and uninvolved serum free light chains if this is the only measurable disease outside of the bone marrow

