10.2.4 Progression-free Survival

Progression-free survival will be calculated from the time of enrollment until the development of progressive disease or death from any cause, whichever occurs first. Patients who elect to undergo high dose chemotherapy followed by autologous stem cell transplantation will not be included in an analysis of progression-free survival.

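### Section 5.9.1 requires two consecutive assessments even for new lesions and hypercalcemia, so clear clinical progression may go uncounted and PFS can be overstated

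*Combined protocol and SAP*

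**What the plan says.** **Definition of PD (Section 5.9.1).** Progression "requires any of the following, confirmed on two consecutive assessments". Two lists follow, joined by an and/or. The first holds the 25% increases in serum M-component, urine M-component, free light chains and marrow plasma cells. The second begins "Definite development of new bone lesions or soft tissue plasmacytomas", extends to definite growth of existing lesions, and ends with "Development of hypercalcemia (corrected serum calcium >11.5 mg/100 ml) that can be attributed solely to the plasma cell proliferative disorder". Neither list is exempt from the lead-in. On timing, the treating physician decides when to repeat, and "there is no need to wait until the next scheduled response assessment".

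**Relapse at entry (Section 5.3.2).** The biochemical list opens with "An increase of 25% from lowest response value in any one or more of the following, verified on two consecutive measurements". It has the same four limbs, marrow included. The clinical list that follows carries no such condition.

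**Response (Section 7).** All categories need two consecutive blood and urine assessments, with no repeat of marrow biopsies, and "no evidence for progressive or new bone lesions if radiographic studies were performed". SD is the remainder: neither a response nor PD.

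**Schedule (Section 2).** Footnote 13 says that if PD is suspected, "response may be re-assessed through repeat of relevant lab tests at any time before the next planned assessment for confirmation". The skeletal survey is marked at screening only; footnote 2 adds a repeat every 12 months, or sooner for symptoms. The discontinuation column has M-protein tests, a metabolic panel and a response assessment, but no survey. The follow-up column has only later anti-cancer treatment and survival.

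**PFS (Sections 10.2.4 and 10.3).** Time runs from enrollment "until the development of progressive disease or death from any cause, whichever occurs first" and is reported by Kaplan-Meier. No rule covers unconfirmed progression, new therapy before confirmation, or which assessment dates the PD.

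**The concern.** Laboratory progression can usually be confirmed by drawing blood again. A clinical sign may be treated before anyone looks a second time: hypercalcemia is corrected, a lesion is irradiated (Section 5.8.2 permits palliative radiation outside the pelvis), or the patient moves to other therapy without another survey. Under the literal wording of 5.9.1 such a patient has not progressed.

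Two outputs are exposed. In PFS, the patient either stays event-free until death or is censored, depending on a choice that the plan does not make; both lengthen the curve. In best response, the patient can be listed as SD, because the new lesion blocks a response under Section 7 while 5.9.1 withholds PD. Section 9.1 allows the first report once the last patient has been on trial for three cycles, so later deaths may not yet have restored the missing events.

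**Working it through.** **Step 1: scope of the confirmation wording.**

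| Place | Laboratory and marrow criteria | Lesions, plasmacytomas, hypercalcemia |
|---|---|---|
| 5.3.2 (relapse at entry) | two measurements | no repeat asked for |
| 5.9.1 (PD, hence PFS) | two assessments | two assessments |
| 7 (response) | two blood and urine assessments; marrow not repeated | one adverse radiographic finding blocks a response |

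**Step 2: two invented records, read literally.**

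- Calcium 12.4 mg/100 ml, attributed solely to myeloma, is treated and is 9.8 at the next assessment. There is no second positive assessment, so no PD.
- M-protein is down 60%, one survey shows new lytic lesions, and other therapy starts without a second survey. Section 7 refuses a response, 5.9.1 refuses PD, and the remainder category is SD. The discontinuation visit repeats laboratory tests but not imaging, and follow-up schedules no disease assessment.

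**Step 3: illustrative size.** The documents state no PFS target, event count or power, so there is no figure to reproduce. Inputs:

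- Illustrative true medians *m* from Section 3.3: 6 and 12 months (the ends of the PFS range quoted there) and 11.1 months (the time to progression of the lenalidomide-dexamethasone arm).
- *f*, the share of first progressions that are clinical only and never confirmed. The documents do not give it, so it is **assumed**. If 10-25% of first progressions show only clinically and half of these lack a second positive assessment, *f* = 0.5 × 10% to 0.5 × 25% = 5-12.5%. The table runs from 0 to 30%.
- Exponential PFS, with *f* constant over time and every first event taken as a progression (a simplification).

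A. Lost events censored at new therapy: the event hazard falls to (1 − *f*)λ, so the apparent median is *m*/(1 − *f*). At 5%, 1/0.95 = 1.05; at 12.5%, 1/0.875 = 1.14. For *m* = 11.1 these give 11.7 and 12.7 months.

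B. Lost events counted only at death: survival after progression is taken as exponential with median 29.6 − 11.1 = 18.5 months, a rough difference of medians from Section 3.3. With λ = ln 2/*m* and μ = ln 2/18.5, solve S(t) = 0.5 for
S(t) = (1 − *f*)e^(−λt) + *f*(μe^(−λt) − λe^(−μt))/(μ − λ).

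Apparent median PFS in months:

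| *f* | A, *m* = 6 | A, 11.1 | A, 12 | B, 6 | B, 11.1 | B, 12 |
|---|---|---|---|---|---|---|
| 0 | 6.00 | 11.10 | 12.00 | 6.00 | 11.10 | 12.00 |
| 5% | 6.32 | 11.68 | 12.63 | 6.41 | 11.77 | 12.71 |
| 10% | 6.67 | 12.33 | 13.33 | 6.86 | 12.50 | 13.49 |
| 20% | 7.50 | 13.87 | 15.00 | 7.97 | 14.19 | 15.25 |
| 30% | 8.57 | 15.86 | 17.14 | 9.40 | 16.18 | 17.32 |

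Among the 16-22 patients at the HTLD / HTLD-CKD (Section 10.2.3), *f* of 5-12.5% is at most 0.05 × 16 = 0.8 to 0.125 × 22 = 2.75 patients, and only if all of them progress.

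**Step 4: set against sampling error.** With *d* events, the 95% interval for an exponential median is about a factor exp(1.96/√*d*) either way: exp(1.96/√16) = 1.63 and exp(1.96/√22) = 1.52. A shift of 5-14% is well inside that.

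**The case against.** A reader might infer that the plan discards unconfirmed clinical progressions and that reported PFS will therefore be too long. The documents do not go that far. Nothing says such a patient is dropped or censored; 10.2.4 and 10.3 are silent. Section 5.9.1 sets no minimum interval, so a second assessment can come before treatment, and metabolic panels are weekly in cycles 1-6. Surveys are not confined to the yearly date: footnote 2 brings them forward for symptoms, and Section 7 asks for imaging on suspicion of bone progression. Entry requires measurable disease, so some clinical progressions will also be confirmed by laboratory values, and death still counts. Footnote 13 speaks only of laboratory repeats, so whether imaging was meant to be confirmed is itself unclear.

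All of that stands, and it makes the effect possible rather than certain. It does not remove the problem. Freedom over timing changes when the repeat is done, not whether it is required, and neither discontinuation nor follow-up schedules the image that would supply it.

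A second stronger inference is that response results are distorted. RR and CBRR contain neither SD nor PD, so moving a patient between those two changes neither rate. Only the tabulation of best response is touched.

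Finally, PFS is a secondary, descriptive endpoint with no comparator or test. That limits the importance of the point, and it stands too.

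**Conclusion.** The point holds as a drafting defect with a one-directional risk. Read literally, 5.9.1 requires a repeat for clinical signs that 5.3.2 accepts without one, and 10.2.4 does not settle how an unrepeated sign is counted or dated. Any resulting error lengthens PFS. It is zero if every repeat is prompt and positive and the first date is used. It is about 5-14% of the median if 5-12.5% of progression events are lost and censored, and slightly more at the same share if they count only at death. Those shares are assumptions, and the documents cannot narrow them, so a flat statement that PFS is overstated is not supported.

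No error rate, sample size or dose decision is affected. The correction is still worth making, because the bias runs one way and is cheap to prevent.

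**What to change.** For endpoint derivation only, amend 5.9.1 / 10.2.4 as follows:

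1. Keep the two-consecutive-assessment condition for the four biochemical limbs that 5.3.2 lists: serum, urine, free light chains and marrow plasma cell percentage. Marrow must be named, because patients measurable only in marrow are eligible. State which of the two dates is the event date; 10.2.3 already uses the first for responses.
2. For PFS and best response, count a definite new or enlarged bone lesion or plasmacytoma, or hypercalcemia attributed solely to myeloma, as PD on first documentation, dated that day.
3. Report PFS under the confirmed-only definition as a sensitivity analysis, stating how new therapy before confirmation is handled there.

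The cost is a few sentences and one extra descriptive analysis, with no added test. The downside is that an occasional unconfirmed finding becomes an event and PFS is slightly shorter. PD also triggers stopping of treatment under 5.9; how that rule should relate to the endpoint definition is for the investigators to reconcile.

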5.10 Follow-Up

Subjects who discontinue treatment for any reason, will be followed every 3 months for 3 years from study entry (if patients are no longer treated at this Institution attempts will be made to obtain information over the phone as per Schedule of Assessments, Section 2). Patients, who stay on protocol therapy will be followed at least every 2 months according to schedule of study assessments (2) for 3 years from study entry. At treatment discontinuation, off study evaluations per the Schedule of Assessments, Section 2, will be done. In addition, subjects will undergo a safety assessment approximately 28 days post the last dose of protocol therapy.

6 Adverse Events

6.1 Serious Adverse Event (SAE) Definition

A serious adverse event is one that at any dose (including overdose):

- Results in death
- Is life-threatening¹

- Requires inpatient hospitalization or prolongation of existing hospitalization
- Results in persistent or significant disability or incapacity²
- Is a congenital anomaly or birth defect
- Is an important medical event³
- Pregnancy

¹“Life-threatening” means that the subject was at immediate risk of death at the time of the serious adverse event; it does not refer to a serious adverse event that hypothetically might have caused death if it were more severe.

²“Persistent or significant disability or incapacity” means that there is a substantial disruption of a person’s ability to carry out normal life functions.

³Medical and scientific judgment should be exercised in deciding whether expedited reporting is appropriate in situations where none of the outcomes listed above occurred. Important medical events that may not be immediately life-threatening or result in death or hospitalization but may jeopardize the patient or may require intervention to prevent one of the other outcomes listed in the definition above should also usually be considered serious. Examples of such events include allergic bronchospasm requiring intensive treatment in an emergency room or at home, blood dyscrasias or convulsions that do not result in inpatient hospitalization, or the development of drug dependency or drug abuse. A new diagnosis of cancer during the course of a treatment should be considered as medically important.

6.2 Adverse Drug Reaction Reporting

Toxicity will be scored using CTCAE Version 4.0 for toxicity and adverse event reporting. A copy of the CTCAE Version 4.0 can be downloaded from the CTEP homepage (<HTTP://CTEP.INFO.NIH.GOV>). All appropriate treatment areas should have access to a copy of the CTCAE Version 4.0. All Grade 3 and 4 adverse clinical experiences, whether observed by the investigator or reported by the patient, must be recorded, with details about the duration and intensity of each episode, the action taken with respect to the test drug, and the patient’s outcome. The investigator must evaluate each adverse experience for its relationship to the test drug and for its seriousness.

The investigator must appraise all abnormal laboratory results for their clinical significance. If any abnormal laboratory result is considered clinically significant, the investigator must provide details about the action taken with respect to the test drug and about the patient’s outcome.

6.2.1 Dose Limiting Toxicity Reporting

Dose limiting toxicity (DLT) is defined as one of the following drug-related toxicities occurring during the first 28-day cycle (if a DLT is attributed to progressive disease, it will not be counted as a DLT):

- Any CTCAE v.4.0 grade ≥ 3 non hematologic toxicity (including febrile neutropenia)
 - For nausea, vomiting, or diarrhea, subjects must have a Grade 3 or 4 event that persists at this level despite the use of optimal symptomatic treatment, in order for these events to be considered a DLT
 - Grade 4 transaminitis (serum transaminase $> 20 \times$ upper limit of normal [ULN]) is a DLT, while Grade 3 transaminitis (serum transaminase $> 5 \times$ and $\leq 20 \times$ ULN) must be present for ≥ 7 days to be considered a DLT
 - Grade 3 or 4 venous thromboembolic events are not considered to be DLTs as long as anticoagulant therapy can be administered (see Section 6.5.3 and 6.6.2)
 - Grade 3 or 4 hypokalemia, hypophosphatemia, hypomagnesemia or hyponatremia that responds to electrolyte supplementation within 7 days would not qualify as a DLT.
- CTCAE v.4.0 grade ≥ 4 neutropenia or thrombocytopenia that does not resolve to grade ≤ 3 within seven days of holding azacitidine and lenalidomide.

The PI has to be informed about the occurrence of DLT within one working day after the sub investigator or nurse becomes aware of it. The PI may not allow further accrual at a given dose level once two patients have developed DLT. The PI has to inform Celgene within 5 working days of any DLT with a brief description of the nature of the DLT.

6.2.2 Pregnancies

Pregnancy of a female subject or the female partner of a male subject occurring while the subject is on lenalidomide or azacitidine or within 4 weeks after the subject's last dose of lenalidomide or azacitidine are considered expedited reportable events. If the subject is on lenalidomide or azacitidine, both drugs are to be discontinued immediately and the subject is to be instructed to return any unused portion of lenalidomide to the Investigator. The pregnancy must be reported to Celgene Drug Safety within 24 hours of the Investigator's knowledge of the pregnancy by phone and facsimile using the SAE Form.

The Investigator will follow the pregnant female until completion of the pregnancy, and must notify Celgene Drug Safety of the outcome as specified below. The Investigator will provide this information as a follow-up to the initial SAE.

If the outcome of the pregnancy meets the criteria for immediate classification as a SAE (i.e., spontaneous abortion [any congenital anomaly detected in an aborted fetus is to be documented], stillbirth, neonatal death, or congenital anomaly), the Investigator should follow the procedures for Expedited Reporting of SAEs to Celgene (i.e., report the event to Celgene Drug Safety by facsimile within 24 hours of the Investigator's knowledge of the event).

Any suspected fetal exposure to lenalidomide or azacitidine must be reported to Celgene within 24 hours of being made aware of the event. The pregnant female should be referred to an obstetrician/gynecologist experienced in reproductive toxicity for further evaluation and counseling.

All neonatal deaths that occur within 30 days of birth should be reported, without regard to causality, as SAEs. In addition, any infant death after 30 days that the Investigator suspects is related to the *in utero* exposure to lenalidomide or azacitidine should also be reported.

In the case of a live "normal" birth, Celgene Drug Safety should be advised as soon as the information is available.

6.2.3 Celgene Drug Safety Contact Information:

Celgene Corporation
Drug Safety
[name]
[name]

Toll Free: [contact]
[contact]
[contact]
e-mail: [contact]

